### 7.3 End-of-trial definition

A subject is considered to have completed the trial if they have completed all periods of the trial including the safety follow-up visit at week 32 (see Section 11.8 for data to be recorded on the end-of-trial form).

The end of the trial is defined as the date of the last visit of the last subject in the trial.

Final collection of data for the primary endpoint occurs at week 4. Therefore, the primary completion date is defined as the date of last week 4 visit for the last subject in the trial.

## 8 Trial population

Trial ID: LP0145-2274

## 8.1 Subject eligibility

The investigator should only include subjects who meet all eligibility criteria, are not put at undue risk by participating in the trial and can be expected to comply with the protocol.

The subject's eligibility for the clinical trial must be verified according to the inclusion and exclusion criteria at visits specified in Panel 2. It will be recorded in the electronic case report form (eCRF) if the subject has met all the inclusion criteria and none of the exclusion criteria.

Any implementation of national requirements/law for the subject's participation in the clinical trial will be ensured and described in submission documentation to regulatory authorities and IRBs/IECs, as applicable.

#### 8.2 Inclusion criteria

The subjects must fulfil all of the following criteria to be eligible for the trial:

- 1. Signed and dated informed consent has been obtained prior to any protocol-related procedures.
- 2. 18 64 years old (both included) at screening.
- 3. Diagnosis of AD [as defined by the AAD Consensus Criteria [43] that has been present for ≥1 year prior to screening.
- 4. Subjects who have a recent history (within 6 months before screening) of inadequate response to treatment with topical medication, or for whom topical treatments are otherwise medically inadvisable.
  - Inadequate response is defined as failure to achieve and maintain remission or a low disease activity state (comparable to IGA 0=clear to 2=mild) despite treatment with a daily regimen of TCS of medium to higher potency (±TCI as appropriate), applied for at least 28 days or for the maximum duration recommended by the product prescribing information (e.g., 14 days for super potent TCS), whichever is shorter.
  - Subjects with documented systemic treatment or phototherapy for AD in the past 6 months are considered as inadequate responders to topical treatment and are potentially eligible for trial inclusion after appropriate washout.
- 5. EASI score  $\geq$ 12 at screening and  $\geq$ 16 at baseline.
- 6. vIGA-AD score  $\geq 3$  at screening and baseline.
- 7. Body surface area (BSA) of AD involvement ≥10% at screening and baseline.

Version: 5.0

8. Worst Daily Pruritus NRS (weekly average) of ≥3 points at baseline.

NOTE: The baseline weekly average will be calculated from daily assessments of itch severity during the 7 days immediately preceding randomisation. A minimum of 4 daily itch scores out of the 7 days is required to calculate the baseline average score. Only for subjects who do not have at least 4 daily itch scores reported during the 7 days immediately preceding the planned randomisation date, randomisation can be postponed until the requirement of 4 daily entries is met, but without exceeding the 28-day maximum duration for screening.

- 9. Subject agrees to apply an emollient twice daily (or more frequently, if needed) to AD lesional and non-lesional skin for at least 7 days before baseline.
- 10. A woman of childbearing potential\* must have a negative serum pregnancy test at screening and a negative urine pregnancy test at baseline.
- 11. A woman of childbearing potential\* must use a highly effective\*\* form of birth control throughout the trial and at least for 18 weeks after last administration of IMP.
  - \* A woman of childbearing potential is defined as a female subject aged  $\geq 12$  years old or a younger girl who, at the discretion of the investigator, is deemed to be of reproductive potential. A woman is defined as not being of childbearing potential if she is postmenopausal (at least 12 months with no menses without an alternative medical cause prior to screening), or surgically sterile (hysterectomy, bilateral salpingectomy, or bilateral oophorectomy).
  - \*\*A highly effective method of birth control is defined as one which results in a low failure rate (less than 1% per year) such as bilateral tubal occlusion, intrauterine device (IUD), intrauterine hormone-releasing system (IUS), combined (oestrogen- and progestogen-containing) hormonal contraception associated with inhibition of ovulation (oral, intravaginal, transdermal), progestogen-only hormonal contraception associated with inhibition of ovulation (oral, injectable, implantable), sexual abstinence (when this is in line with the preferred and usual life style of the subject and not just being without a current partner), same-sex partner, or vasectomised partner (given that the subject is monogamous).

### 8.3 Exclusion criteria

Subjects are not eligible for the trial if they violate any of the following criteria:

1. Treatment with systemic immunosuppressive/immunomodulating medication (excluding systemic antihistamines if taken at stable dose already before baseline), e.g., JAK inhibitors, immunoglobulin/blood products within 2 weeks or 5 half-lives prior to baseline, whichever is longer.

- 2. Treatment with systemic corticosteroids within 4 weeks prior to baseline NOTE: Inhaled or intranasal steroids equivalent to doses including and up to 500 μg beclometasone (or equivalent) daily is allowed.
- 3. Intake of nonsteroidal anti-inflammatory drugs (NSAIDs) within 1 week prior to baseline.
  - NOTE: Intake of paracetamol will be allowed.

Trial ID: LP0145-2274

- 4. Treatment with biologics within 5 half-lives (if known) or 16 weeks prior to baseline, whichever is longer.
- 5. Allergen immunotherapy within 4 weeks prior to baseline.
- 6. Treatment with TCS, TCI, topical PDE-4 inhibitor, or other topical prescription treatments (i.e., medications or prescription emollients/moisturisers (other than the ones allowed during treatment period) used for the treatment of AD) within 1 week prior to baseline.
  - *NOTE:* Subject may be rescreened (once) if failed for this criterion (see Section 8.4).
- 7. Use of tanning beds or phototherapy (narrow band ultraviolet B [NBUVB], ultraviolet B [UVB], ultraviolet A1 [UVA1], psoralen + ultraviolet A [PUVA]) within 4 weeks prior to baseline.
- 8. Treatment with a live (attenuated) vaccine within 12 weeks prior to baseline.
- 9. Active dermatologic condition that could confound the diagnosis of AD or interfere with assessment of the treatment.
- 10. History of malignancy within 5 years prior to baseline, apart from non-metastatic basal cell carcinoma, squamous cell carcinoma of the skin, or cervical carcinoma in-situ, considered cured by the standard of care.
- 11. Clinically significant active chronic or acute infection requiring systemic treatment within 4 weeks prior to baseline that may compromise the safety of the subject.

  NOTE: Subject may be rescreened (once) after infection resolves (see Section 8.4).
- 12. Skin infection within 1 week prior to the baseline visit.

  NOTE: Subject may be rescreened (once) after infection resolves (see Section 8.4).
- 13. Current or recent (within 2 years prior to baseline) gastrointestinal ulcers.
- 14. History of any of the following: anaphylaxis, immune complex disease, pancreatic disease, inflammatory bowel disease or known or suspected history of immunosuppressive disorder.

- 15. Known or suspected hypersensitivity to any component(s) of the IMPs.
- 16. Known or suspected hypersensitivity to local anesthetics.
- 17. Presence of hepatitis B or C infection at screening. These are defined as: 1) Positive hepatitis C Ab, or 2) Positive HBsAg, or 3) Negative anti-HBs Ab AND positive anti-HBc Ab.
- 18. History of human immunodeficiency virus (HIV) infection or positive HIV serology at screening.
- 19. Subject has a positive or indeterminate *Mycobacterium tuberculosis* IFN-γ release assay test or a positive purified protein derivative (PPD) test at screening.

  NOTE: The PPD test is only accepted if it is a requirement from local health authorities.
- 20. Current diagnosis of diabetes.
- 21. Clinically significant abnormalities detected on vital signs or ECG (apart from 1st degree atrioventricular (AV) block that is allowed).
- 22. Serious heart conditions (e.g., heart failure, coronary artery disease, congenital heart disease, cardiomyopathies, and/or pulmonary hypertension).
- 23. Chronic lung diseases (e.g., chronic obstructive pulmonary disease, idiopathic pulmonary fibrosis, and/or cystic fibrosis).
- 24. Acute asthma, acute bronchospasm, moderate to severe asthma [as defined by GINA guidelines [44]].
- 25. Obesity (BMI  $\geq$ 35).
- 26. Subject has laboratory abnormalities that, in the opinion of the investigator, will prevent the subject from completing the trial or interfere with the analysis of results.
- 27. Subject is pregnant or lactating.
- 28. Subject has a history of chronic alcohol or drug abuse within 12 months prior to screening, or any condition associated with poor compliance as judged by the investigator.
- 29. Employees of the trial site or any other individuals directly involved with the planning or conduct of the trial, or immediate family members of such individuals.
- 30. Any disorder\* at screening and/or baseline, which is not stable in the opinion of the investigator, and could:
  - a. Affect the safety of the subject throughout the trial.

Trial ID: LP0145-2274 Date: **04-Jan-2023** Version: 5.0 Page 50 of 129

b. Influence the findings of the trial.

- c. Impede the subject's ability to complete the trial.
- \*Examples include but are not limited to endocrine, gastrointestinal, hepatic, immunological, infectious, metabolic, musculoskeletal, neurological, and major physical impairment.
- 31. Any significant abnormal finding\* at baseline and/or screening which may in the opinion of the investigator:
  - a. Put the subject at risk because of their participation in the trial.
  - b. Influence the results of the trial.
  - c. Influence the subject's ability to complete the trial.
  - \*Examples include clinically significant abnormal vital sign, physical examination, ECG, and laboratory result.
- 32. Treatment with any non-marketed drug substance (that is, an agent which has not yet been made available for clinical use following registration) within the last 4 weeks or 5 half-lives prior to baseline, whichever is longer.
- 33. Current participation in any other interventional clinical trial.
- 34. Previously randomised in this clinical trial.
- 35. Subjects who are legally institutionalised.

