#### Clinical data

One first-in-human (FiH) clinical trial with LEO 138559 was completed (LP0145-1315) and further trials (PK and proof of concept) with LEO 138559 are ongoing.

The FiH trial was a randomised, double-blind, placebo-controlled, multi-centre trial to evaluate the safety, tolerability, PK, and PD of LEO 138559 in healthy volunteers (HV) and subjects with moderate to severe AD. The trial contained a single-ascending dose (SAD) and multiple-ascending dose (MAD) part with overall 51 subjects. SAD were administered intravenously (IV) and subcutaneously (SC) in healthy volunteers (HV). MAD were administered SC in HV and patients with AD. In patients with AD (data from 8 patients were available), a reduction in disease severity based on individual EASI scores was observed for LEO 138559 compared with placebo.

No fatal events, no SAEs, and no severe AEs were reported during the trial. No AE patterns giving rise to any concerns have been reported from the 35 subjects who received LEO 138559. 19 HV were exposed to single doses of LEO 138559 (IV in 11 HV, and SC in 8 HV), and 12 patients with AD and 4 HV were exposed to multiple SC doses of LEO 138559.

Among a total of 17 adverse events considered as possibly or probably related to the treatment reported in 8 subjects either receiving single or multiple doses of LEO 138559, the most frequently reported adverse events were infections and infestations observed in 6 of 35 subjects exposed to LEO 138559 and considered mild to moderate in severity at most.

Trial ID: LP0145-2274 Date: **04-Jan-2023** 

Page 36 of 129

Version: 5.0

Furthermore, nervous system disorders were reported for a total of 3 subjects, 2 of them having a single episode of headache and a 3rd subject reported to suffer from dizziness. In addition, 2 subjects developed skin and subcutaneous disorders. All other adverse events were reported only once without any clustering or trends for a special type of events.

Overall, there were no clinically relevant treatment effects on vital signs and clinical laboratory parameters. No severe AEs were reported. No risks for humans have been identified at the dose levels of up to 450 mg LEO 138559 dosed weekly (the selected dose for biweekly dosing in the present trial) tested to date.

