#### 11.6.3 Skin biopsies

Lesional skin biopsies from subjects treated with LEO 138559 or Dupixent® will be evaluated by single-cell RNASeq analysis, a technique which enables evaluation of global gene expression in single cells and which has previously been used in a study in subjects with AD treated with Dupixent® [52]. Effects of LEO 138559 on single-cell transcriptomics have not been evaluated to date. Histological analysis will also be performed, on the same biopsies.

One 5 mm skin punch biopsy will be taken at each time-point specified in the schedule of trial procedures (Section 4) for analysis of differentially expressed genes analysed by single cell RNA sequencing and for AD biomarker analysis.

At baseline, the biopsy will be taken from a representative lesional area. At the end-of-treatment visit (or early IMP termination visit, if applicable) the same lesional area as at baseline ("original lesional area") will be sampled. Note that the lesion sample at the end-of-treatment (or early IMP termination visit, if applicable) should be taken from the original lesional area, even if this lesion clears during the trial. At the other sampling timepoint a biopsy may be taken from any other representative lesion.

Photographs will be taken of the biopsy sites prior to each biopsy sampling.

A check of skin biopsy wound healing including removal of suture, if applicable, will be performed at the next trial visit. After the biopsy at week 16 visit, subjects will be asked to return to site for suture removal two weeks later (week 18) or alternatively to have the sutures removed by their general practitioner, as preferred by subject.

Collection, handling, and shipment instructions for skin biopsy samples for single cell RNA sequencing and evaluation of biomarkers are provided in a separate laboratory manual.

Skin biopsy single cell RNA sequencing and biomarker data will be described in detail in a separate report appended to the CTR

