# 12 Scientific rationale for trial design and appropriateness of

# 12.1 Scientific rationale for trial design

assessments

LP0145-2274 is a randomized, double-blinded, active comparator-controlled, 16-week, single-site exploratory, mechanistic trial designed to evaluate the effect on the molecular signature of SC administered LEO 138559 450 mg Q2W compared with Dupixent® Q2W in adults with moderate to severe AD.

The primary endpoint is selected to gain information about the mode of action of LEO 138559 and the influence of blocking of IL-22 pathway on gene expression in lesional skin.

Based on PK, PD, and safety results of the FiM trial with LEO 138559 (LP0145-1315), the dose regimen LEO 138559 450 mg Q2W was selected for investigation in this trial. In addition to the Q2W dosing schedule, an additional dose of IMP will be given to the subjects at week 1 to reach steady state exposure early in the treatment period. According to a PK model developed based on preliminary data from the FiM trial, the additional dose given at week 1 should allow 75% of steady state exposure to be reached already after 3 weeks of treatment. The 16-week treatment period was selected to ensure sufficient time to evaluate the impact of LEO 138559 on disease severity as AD. Further, given the expected half-life, dosage, and dosing frequency of LEO 138559, it is expected that LEO 138559 achieve steady state concentration before the end of this period and a maximum therapeutic effect will be achieved by this time. A safety follow-up period of 16-week after last dose of IMP is considered an appropriate length as serum concentrations of LEO 138559 are expected to be declined to nondetectable levels (below the lower limit of quantification) in most subjects at that timepoint.

The use of Dupixent® as a comparator will serve as reference to evaluate the mode of action, efficacy and safety of LEO 138559. The comparison with an approved immunoregulatory agent that selectively and simultaneously inhibits IL-4 and IL-13 allows for an evaluation of similarity or differences in the mechanistic effect. Dupixent® will be administered according to the prescription instructions (standard of care) for adult subjects with moderate to severe AD with an initial dose of 600 mg followed by Q2W injections with 300 mg.

Trial ID: LP0145-2274 Date: **04-Jan-2023** 

Page 87 of 129

Version: 5.0

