33	Current participation in any other interventional clinical trial.	To ensure safety of subjects and ensure lack of confounding of measurements (e.g. efficacy, PK, and PD).
34	Previously randomised in this clinical trial.	To ensure integrity and validity of the trial data due to the possibility of duplicate subject entries.
35	Subjects who are legally institutionalised.	To ensure compliance with Declaration of Helsinki [37].

Trial ID: LP0145-2274

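### No criterion bars earlier exposure to LEO 138559 in another trial, so a drug-experienced subject may enter after washout with antibodies or tissue effects that washout need not remove

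*Combined protocol and SAP*

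**What the plan says.** Exclusion 34 in Section 8.3 removes anyone "Previously randomised in this clinical trial". Appendix 5 gives its purpose as protecting the data "due to the possibility of duplicate subject entries". It is a rule against double entry, not a rule on exposure to the drug.

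Earlier treatment is handled by intervals:

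- Exclusion 4: "Treatment with biologics within 5 half-lives (if known) or 16 weeks prior to baseline, whichever is longer". LEO 138559 is a monoclonal antibody (Section 5.2), so this applies to it.
- Exclusion 32, on non-marketed drugs: "within the last 4 weeks or 5 half-lives prior to baseline, whichever is longer".
- Exclusion 33 bars subjects who are at present in another interventional trial.
- Exclusions 14 and 15 bar a history of anaphylaxis and known or suspected hypersensitivity to the trial products.

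Section 5.2 reports that 12 patients with atopic dermatitis received multiple doses of LEO 138559 in the completed first-in-human trial, and that "further trials (PK and proof of concept) with LEO 138559 are ongoing". On the purpose of the biopsies, Section 11.6.3 says: "Effects of LEO 138559 on single-cell transcriptomics have not been evaluated to date".

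**The concern.** Read together, these criteria leave a gap. Someone who has received LEO 138559, has passed the drug-free interval and is in no other trial is not excluded. Such people exist, and they have the disease under study.

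The interval is set by how fast the drug leaves serum. Nothing in the documents says that antibodies against the drug, or changes in skin after earlier treatment, go at the same rate. Two readouts are exposed:

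- **Primary endpoint.** This is change from baseline in lesional biopsies, in a trial meant to give the first single-cell account of this drug. A drug-experienced subject may not have a drug-naive baseline.
- **ADA endpoint.** Antibodies brought into the trial would be reported alongside antibodies that arise during it.

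The sponsor already accepts the principle. Appendix 5 justifies exclusion 32 partly by the need to avoid confounding of efficacy, PK and PD measurements.

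**Working it through.** There is no power calculation to reproduce; Section 14.1 says the sample size does not rest on one. The stated numbers agree with each other: 12 × 2/3 = 8 and 12 × 1/3 = 4 (Sections 7.2 and 14.1). For the first-in-human trial, 19 + 12 + 4 = 35 exposed (Section 5.2). Of these 35, only the 12 patients with atopic dermatitis could meet inclusion 3.

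**Drug-free interval.** The half-life is 21 to 25 days (Section 5.2, Pharmacokinetics).

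- Five half-lives: 5 × 21 = 105 days (15.0 weeks); 5 × 25 = 125 days (17.9 weeks).
- Exclusion 4, the longer of this and 112 days: 112 to 125 days, or 16.0 to 17.9 weeks.
- Exclusion 32, the longer of this and 28 days: 105 to 125 days. It adds nothing beyond exclusion 4.

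**Drug left at the end of the interval.** Assuming first-order decline at a constant half-life, the fraction is 2^(−days/half-life): 2^(−112/21) = 2.5% and 2^(−125/25) = 3.1%.

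**Reach of the medication history.** Take three months as about 13 weeks. Section 9.6 counts from screening, so with up to 4 weeks of screening it reaches at most 13 + 4 = 17 weeks before baseline. Note m to Panel 2 counts from baseline and reaches 13 weeks. An eligible drug-experienced subject had the last dose at least 16.0 to 17.9 weeks before baseline. The record may therefore miss exactly the subjects in question. Section 14.3.2 summarises previous treatments for atopic dermatitis, but the protocol sets no look-back for them.

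**ADA rule.** ADA is assessed at weeks 0, 4, 8, 12, 16 and 32. Section 14.3.9.5 calls a subject persistent positive after positive results at two consecutive ADA visits. Weeks 0 and 4 are consecutive ADA visits. A subject who arrives positive and is still positive at week 4 therefore meets the definition, although the first result precedes any dose in this trial. No rule separates pre-existing from treatment-emergent ADA.

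**Weight of one subject.** 1/8 = 12.5% of the LEO 138559 arm; 1/4 = 25% of the comparator arm.

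**Where such subjects would fall.** Let k of the 12 be drug-experienced. The documents do not give k, and it may be 0; the values below are assumptions. With an 8:4 split, the chance that at least one is in the LEO 138559 arm is 1 − C(4,k)/C(12,k).

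| k (assumed) | Chance of at least one in LEO 138559 arm | Expected number there (k × 8/12) |
|---|---|---|
| 1 | 1 − 4/12 = 67% | 0.67 |
| 2 | 1 − 6/66 = 91% | 1.33 |
| 3 | 1 − 4/220 = 98% | 2.0 |

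**The case against.** The case for leaving the criteria alone has weight.

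- **No occurrence is shown.** Nothing says that the Austrian site or its patients took part in earlier LEO 138559 trials, or that such patients will be sought. This stands.
- **Residual drug is a minor matter.** About 2.5% to 3.1% would remain, and Section 12.1 expects, 16 weeks after the last dose, "nondetectable levels (below the lower limit of quantification) in most subjects at that timepoint". PK is sampled before dosing at week 0, so any remainder would be seen. This stands, and the point does not rest on residual drug.
- **Known sensitisation is covered** by exclusions 14 and 15. This stands for recognised reactions. It does not catch antibodies without symptoms. ADA is measured at week 0, but a positive result does not exclude.
- **Washout is the protocol's approach to every biologic**, including earlier use of the comparator. That is consistent. But LEO 138559 is the drug whose first single-cell description is sought and whose immunogenicity the ADA samples assess, so earlier exposure to it bears directly on both.
- **The analysis is descriptive and individual data are plotted** (Sections 14.3.4 and 14.3.5). True, but a plotted subject cannot be recognised as drug-experienced if the exposure was never recorded. The definition of treatment-emergent adverse events is anchored to the first dose in this trial and is not disturbed.

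A reader might also infer three stronger things that the documents do not support:

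- **That earlier responders would be pre-selected.** No selection mechanism is described. Entry requires active disease (EASI of at least 16 and vIGA-AD of at least 3 at baseline), and subjects are then randomised to both arms. The report that 3 of 4 subjects on 450 mg had an EASI reduction of at least 90% does not help: it rests on four people, and selection could raise 75% only to 100%.
- **That participants in ongoing trials may enter.** Exclusion 33 bars them until they have left.
- **That earlier allocation would be unknown because the ongoing trials are double-blind.** Section 5.2 describes only the completed first-in-human trial as double-blind.

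**Conclusion.** The gap is real but small, and closing it is an inexpensive improvement. The criteria permit a subject with earlier LEO 138559 exposure to be randomised after 16.0 to 17.9 weeks without the drug. The plan has no certain way to record that exposure and no rule for ADA already present at week 0. One such subject would carry 12.5% of the LEO 138559 summary or 25% of the comparator summary.

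This rests on two assumptions that the documents neither confirm nor exclude: that at least one such patient would present, and that antibodies or tissue changes can outlast serum drug. If no such patient presents, nothing in the results changes. No sample size, power or error rate is involved, and the text gives no ground for claiming a bias of known direction.

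**What to change.** 1. Reword exclusion 34 to: *Previously randomised in this trial, or previously exposed to LEO 138559 in any clinical trial.* Extend its justification in Appendix 5 to confounding of PD, PK and ADA.
2. Ask at screening about lifetime exposure to LEO 138559, because the 3-month medication history may not reach it. The first-in-human trial was placebo-controlled, so taking part is not the same as exposure; the site may need the sponsor to confirm which applied.
3. If such a subject has already been randomised, flag the subject and show the primary endpoint and ADA results with and without that subject.

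The cost is one phrase in Section 8.3 and its counterpart in Appendix 5, one screening question and a slightly smaller recruitment pool. The rewording changes an eligibility criterion and so needs an amendment; Amendment 1, which changed exclusion criteria, was classed as substantial. Step 3 adds a short set of descriptive tables, and only if it applies.
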